2 STUDY OBJECTIVES

2.1 Primary Objective

Evaluate the efficacy of treatment with high-titer versus low-titer anti-influenza immune plasma as an addition to standard care in subjects hospitalized with severe influenza A.

The primary endpoint will be assessed by the subject's clinical status at Day 7 on a 6-point ordinal scale:

1. Death
2. In the ICU
3. Non-ICU hospitalization, requiring supplemental oxygen
4. Non-ICU hospitalization, not requiring supplemental oxygen
5. Not hospitalized, but unable to resume normal activities
6. Not hospitalized with full resumption of normal activities

2.2 Secondary Objectives

1. Evaluate the efficacy and safety of treatment with high-titer versus low-titer anti-influenza immune plasma as an addition to standard care, using the following parameters:

- The ordinal primary outcome assessed at Days 1, 2, 3, 14, and 28
- Duration of initial hospitalization
- 28-day mortality
- In-hospital mortality during initial hospitalization
- Composite of mortality and hospitalization at Days 7, 14, and 28
- Change from baseline to Day 3 and Day 7 in NEW/PEW score
- Duration of supplemental oxygen use among those requiring oxygen at randomization
- Incidence of new oxygen use during the study
- Duration of ICU stay among those requiring ICU admission at randomization
- Incidence of new ICU admission during the study
- Duration of mechanical ventilation use among those requiring mechanical ventilation at randomization
- Incidence of new mechanical ventilation use during the study
- Duration and severity of ARDS among those meeting the definition of ARDS at randomization
- Incidence and severity of new ARDS during the study
- Duration of ECMO use among those requiring ECMO at randomization
- Incidence of new ECMO use during the study
- Change from baseline to Day 3 and Day 7 SOFA score for age \geq 18 years, and PELOD score for age $<$ 18 years
- Disposition (home, rehabilitation, chronic nursing facility, initial hospitalization ongoing at 28 days, died in hospital) following the initial hospitalization

- Percent of subjects with influenza virus detectable in OP sample at Day 3

2. Compare the plasma and control groups for HAI titers at Days 1, 3, and 7.

3. Evaluate the safety of high titer anti-influenza plasma as compared to low titer plasma as assessed by:

- Cumulative incidence of grade 3 and grade 4 adverse events (AEs)
- Cumulative incidence of serious adverse events (SAEs)

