6.3.1.3 Medical History

The investigator (or designee) will take a medical history following consent and conduct a complete physical examination. The following information should be recorded:

- Day of onset of influenza symptoms
- Influenza vaccination in the current season
- History of chronic medical conditions
- Any acute medical problems from the current hospitalization (including laboratory abnormalities)
- Current use of prescription and OTC medications
- History of allergies
- Additional history to be obtained from pregnant women includes last menstrual period, ultrasonic gestational age (if known), and complications during pregnancy.
- For women who are not of childbearing potential, the reason for this (if known) should be documented.

Medical conditions noted at the time of consent should be recorded in the eCRF. Any conditions that develop after consent should be recorded on the AE page of the eCRF.

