7.3 Efficacy Measures

7.3.1 Ordinal Scale

The ordinal scale is an assessment of the clinical status at the first assessment of a given study day (i.e., at approximately 8AM). The clinical status should be recorded as the subject currently exists, without consideration as to need (i.e., is the subject in the ICU, and not does the subject have medical needs to be in the ICU, or has the subject been discharged home and not is the subject capable at that moment of being discharged to home). The scale is as follows:

1. Death
2. In ICU
3. Non-ICU hospitalization, requiring supplemental oxygen
4. Non-ICU hospitalization, not requiring supplemental oxygen

5. Not hospitalized, but unable to resume normal activities
6. Not hospitalized with full resumption of normal activities

For the purposes of this study, resumption of normal activities refers to resumption of activities that the subject could undertake prior to first onset of symptom(s) of influenza.

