12.2 Sample Size and Power Considerations

The planned sample size for the trial is 150 subjects, randomized in an approximately 2:1 ratio to high-titer versus low-titer anti-influenza plasma. To evaluate the power of the study, the following assumptions were made:

- a. The primary analysis will compare the high-titer and low-titer plasmas using a proportional odds model and a two-sided Type I error rate of 0.05.
- b. It is anticipated that very few of these subjects will be randomized and not start study plasma infusion (and so be excluded from the primary analysis) or be lost to follow-up prior to Day 7 (and so have missing data for the primary endpoint). In addition, power is reduced slightly and hence the effective sample size is reduced by interim analyses reviewed by the DSMB. Conservatively, a 10% reduction in the total sample size from 150 to 135 subjects was made to allow for these issues.
- c. Data from the control arm of IRC002 for adults with influenza A infection, NEW score ≥ 3 , and duration of time from onset of symptoms of influenza to randomization ≤ 6 days, suggests the distribution of subjects in the low-titer arm for the primary endpoint shown in the following table:

Table 12: Anticipated Distribution of Subjects in the Ordinal Scale

| | Low-Titer Arm | High-Titer Arm | |
|---|----------------------|-----------------------|-----------|
| | (Based on IRC 002) | 80% Power | 90% Power |
| Died | 10% | 4.3% | 3.7% |
| In ICU | 35% | 20.4% | 18.4% |
| Non-ICU hospitalization, requiring supplemental oxygen | 25% | 23.6% | 22.6% |
| Non-ICU hospitalization, not requiring supplemental oxygen | 10% | 13.3% | 13.4% |
| Not hospitalized, but unable to resume normal activities | 5% | 7.9% | 8.2% |
| Not hospitalized, but with full resumption of normal activities | 15% | 30.6% | 33.7% |
| Proportional odds ratio comparing high titer to low titer | | 2.50 | 2.88 |

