Based on the above assumptions, the table also shows the type of true difference (assuming proportional odds) that would be detected with 80% or 90% power. For example, the study would have 80% power to detect a proportional odds ratio of 2.50. This is the odds ratio that arises when comparing the proportion not hospitalized and able to resume normal activities in the high-titer arm (30.6%) to that in the low-titer arm (15%). The proportional odds model assumes that the same odds ratio applies to the cumulative proportions moving up the ordinal scale: for example, for the proportion not hospitalized in the high-titer arm ($30.6+7.9=38.5\%$) to that in the low-titer arm ($15+5=20\%$); or for the proportion alive and not in an ICU in the high-titer arm ($30.6+7.9+13.3+23.6=75.4\%$) to that in the low-titer arm ($15+5+10+25=55\%$).

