## **10.3 Disposition**

- a. Table of disposition following initial hospitalization (home without assistance, home with home health care, rehabilitation, chronic nursing facility, initial hospitalization ongoing at 28 days, died during initial hospitalization): Number (%) of subjects in each disposition category, showing also number with missing values (eg due to withdrawal of consent during initial hospitalization). The table will also show the p-value comparing treatments (Wald test from the proportional odds model), as well as the estimated proportional odds ratio comparing treatments with associated 95% CI.

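### The ranked disposition comparison takes no account of residence or care before influenza, and neither document lists that item for collection

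*Protocol*

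**What the plan says.** Disposition after the initial hospitalization is one of the secondary parameters in Protocol 2.2, listed as "Disposition (home, rehabilitation, chronic nursing facility, initial hospitalization ongoing at 28 days, died in hospital"). SAP 10.3 splits the home category and gives six levels, beginning "home without assistance, home with home health care, rehabilitation, chronic nursing facility" and ending with hospitalization still ongoing at Day 28 and death during the initial stay. The analysis is a proportional odds model with a Wald p-value, an odds ratio and a 95% CI. That model needs an order. The order listed puts home with home health care second and chronic nursing facility fourth of six. No covariate is named.

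The items listed for collection do not include pre-illness residence:

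- Protocol 6.3.1.2 (Demographics) has age, sex, ethnicity and race.
- Protocol 6.3.1.3 (Medical History) has symptom onset, vaccination, chronic conditions, medications, allergies, pregnancy items and "Any acute medical problems from the current hospitalization (including laboratory abnormalities").
- Protocol 6.3.3.1 (Baseline Clinical Data) and SAP 6, tables a to n, have no such item either.

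Nothing in Protocol 4.1 to 4.3 excludes people who live in a facility or already receive home care.

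The primary scale is treated differently. Protocol 7.3.1 states that "resumption of normal activities refers to resumption of activities that the subject could undertake prior to first onset of symptom(s) of influenza", so its best category is relative to the subject's own earlier state.

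**The concern.** For someone who lived in a nursing facility before influenza, going back there is ordinarily the best result available. Under SAP 10.3 it occupies the same rank as loss of independence in someone who used to live at home. Such a subject can show benefit only by surviving or by leaving hospital before Day 28. Differences among the better destinations cannot register. A prior home-care user is similarly capped at the second category.

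Two things follow. The odds ratio is pulled toward 1, which costs power. The nursing-facility row also mixes recovery with decline, and without the baseline item a reader cannot separate them, check the arms for chance imbalance, or see whether some sites entered a resident's return as home.

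The endpoint carries some weight. Protocol 1.2.2.4 cites the corresponding IRC002 table (p = 0.029) as supportive. In that table 6 subjects in each arm went to long-term care, and how many of them were returning residents is not stated.

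**Working it through.** **Step 1: reproduce the plan's power figure (primary endpoint).** Inputs from Protocol 12.2: the comparison is made "using a proportional odds model and a two-sided Type I error rate of 0.05"; "a 10% reduction in the total sample size from 150 to 135 subjects was made"; allocation is 2:1, giving 90 v 45; and "the study would have 80% power to detect a proportional odds ratio of 2.50". With the Table 12 distributions and Whitehead's formula:

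- V = n1·n2/(3N) × (1 − Σp̄³), with n1·n2/(3N) = 45 × 90/(3 × 135) = 10.
- The mean category shares p̄ (worst to best) are 7.15, 27.7, 24.3, 11.65, 6.45 and 22.8%, so Σp̄³ = 0.0497 and V = 9.50.
- Power = Φ(ln 2.50 × √9.50 − 1.96) = Φ(0.916 × 3.083 − 1.96) = Φ(0.865) = 80.6%.

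The same formula gives 90.4% at OR 2.88 (stated: 90%). A simulated tie-corrected Wilcoxon test gives 79.7% and 89.5%. The plan's figures reproduce. They refer to the primary scale. No power is stated for disposition.

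**Step 2: check the IRC002 disposition table.** From worst to best (dead, hospice, in hospital at Day 28, long-term care, home with care, home), standard care is 5/1/11/6/6/14 (n = 43) and plasma is 1/0/7/6/7/21 (n = 42). A tie-corrected Wilcoxon test gives p = 0.0287, against 0.029 stated.

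Share in the home categories above long-term care:

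- overall: (13 + 35)/85 = 56%
- standard care: 20/43 = 47%
- plasma: 28/42 = 67%

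**Step 3: power for disposition if a share f were prior facility residents.** f is not in the documents, so it is an assumption shown as a range. Setup:

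- Control shares, best to worst: 33/14/7/8/26/12%. These follow the IRC002 standard-care arm, with hospice left out, long-term care split between rehabilitation and nursing facility by assumption, and the total rescaled.
- High-titer arm by proportional odds shift; 90 v 45; two-sided 0.05; Wilcoxon test (the score-test counterpart of the model); 100,000 trials per row.
- Every resident discharged alive is coded nursing facility.
- *Stratified* is a van Elteren test with resident/non-resident strata and the SAP categories kept.
- *Re-ranked* puts return to the prior residence in the top category.

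| OR | f | As planned | Stratified | Re-ranked |
|---|---|---|---|---|
| 2.50 | 0% | 78.4% | – | – |
| 2.50 | 5% | 75.2% | 77.1% | 77.0% |
| 2.50 | 10% | 72.6% | 76.7% | 76.1% |
| 2.50 | 20% | 67.5% | 75.1% | 73.9% |
| 2.88 | 0% | 88.1% | – | – |
| 2.88 | 5% | 85.6% | 87.2% | 87.0% |
| 2.88 | 10% | 83.3% | 86.8% | 86.4% |
| 2.88 | 20% | 78.6% | 85.8% | 84.8% |

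At OR 2.50 the loss is 3.2, 5.8 and 10.9 points for f = 5%, 10% and 20%. Stratifying returns 1.9, 4.1 and 7.6 of them.

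**Step 4: sensitivity to the setup.** With no rehabilitation level and hospice merged with death, power at OR 2.50 is 78.1% at f = 0, then 75.7%, 73.7% and 69.5% at f = 5%, 10% and 20%. The losses are 2.4, 4.4 and 8.6 points, slightly smaller.

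**The case against.** The strongest reply is that the effect is modest and its main input unknown. At 5% residents or fewer the loss is about 3 points at most and the fix returns about 2. This is one secondary parameter among many, with no power claimed for it. That stands, and it is why the point is minor.

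The upper rows are also hard to square with IRC002. Its 14% in long-term care already includes any returning residents, whereas the simulation adds residents on top. The control share in rehabilitation or nursing facility becomes 0.9 × 15 + 0.1 × 62 = 19.7% at f = 10%, and 0.8 × 15 + 0.2 × 62 = 24.4% at f = 20%. The 20% row is therefore a stress case. In the other direction, the cap on prior home-care users is not modelled.

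It can also be said that recovery relative to the pre-illness state is already captured, because the 6-point scale is analysed at Days 14 and 28 as well. That limits what is lost, but it does not tell a reader what the nursing-facility row of the disposition table means.

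A reader might infer four stronger points that the documents do not support:

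- *A returning resident ranks below most subjects.* On IRC002 figures 56% overall, but only 47% of standard care, were in the home categories. IRC002 also had no separate rehabilitation level and used the last discharge, not the first.
- *The comparison is biased.* Residence precedes randomization, so apart from chance imbalance the effect is dilution.
- *The fix restores the 0%-resident power.* It does not. Residents discharged alive still share one category, so part of the information is lost under either remedy.
- *The item is not recorded and the problem cannot be repaired.* The eCRF is not among the documents, so one can say only that neither document lists it. Protocol 14.1 allows data to be abstracted from medical records.

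**Conclusion.** The point holds as a minor improvement to one secondary analysis. SAP 10.3 ranks disposition without reference to residence or care before influenza, although the plan anchors the top of its primary scale to the pre-influenza state. The consequence is dilution and a category that cannot be interpreted. The size depends on an assumed resident share. At OR 2.50, across the two setups, the loss is about 2 to 3 points at 5%, 4 to 6 at 10% and 9 to 11 at 20%, of which stratification recovers about 2, 4 and 7 to 8 points in the main setup. These figures assume that every resident discharged alive returns to a facility and that the control disposition resembles IRC002 standard care. The primary analysis, the sample size of 150 and the power stated in Protocol 12.2 are untouched. The gain in interpretability does not depend on the assumed share.

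**What to change.** 1. Protocol 6.3.1.3: add one item, usual residence and level of care before this illness (home without help, home with home health care, rehabilitation, chronic nursing facility).
2. SAP 6: tabulate it by arm.
3. SAP 10.3: keep the six categories and the raw destination table, and adjust or stratify the proportional odds model by prior residence and care, merging sparse levels by a rule set in advance. Show the unadjusted odds ratio beside it, and state how a resident's return to a facility is to be coded.
4. As a sensitivity analysis only, rank return to pre-illness residence and level of care as the best outcome. It should not be the main analysis: a resident who returns with marked new dependence would then rank above a previously independent subject who goes home with temporary help. In the simulation it also recovers no more than stratification does.

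The cost is one eCRF field and a few lines in the SAP. For subjects already enrolled, the field has to be filled from medical records. Because the item predates randomization and the study is blinded, doing so late should not introduce bias, though some records may be silent and a missing category is needed.

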3 INVESTIGATIONAL PLAN

3.1 General

Up to 300 subjects are planned for enrollment in order that 150 subjects may be randomized. Randomized adult subjects will receive 2 units of plasma. Randomized pediatric subjects will receive a weight-based infusion of plasma which, depending on the calculated plasma volume, may be one or two infusions. See Section 5.7 for specifics of the plasma dosing. All subjects will be followed through Study Day 28. The study population will consist of males and females hospitalized with severe influenza A.

3.2 Definitions

Definitions for the purpose of this study:

- **Enrolled:** For the purpose of collecting data and samples, and reporting AEs, a subject will be considered enrolled beginning from when the informed consent form is signed until the subject is considered “screen failure”, “discontinued”, or “completed”.
- **Randomized:** For the purpose of study reporting and data analysis, subjects are considered randomized when a randomization number is assigned.
- **Screen Failures:** Subjects are considered screen failures when they meet one of the following criteria after signing consent:
 - Screening tests reveal that the subject is ineligible.
 - Subject withdraws consent before being randomized.
- **Discontinued:** Subjects are considered discontinued when they meet one or both of the following criteria:
 - Subject withdraws consent after being randomized (refer to Section 4.4).
 - Subject is withdrawn by investigator after being randomized (refer to Section 4.5).
- **Completed:** Subjects are considered completed when they are followed through Study Day 28 or followed through to death at or prior to 28 days.

3.3 Overview of Study Design

This randomized, double-blinded, multicenter Phase 3 trial will assess the efficacy and safety of high-titer versus low-titer anti-influenza immune plasma for the treatment of severe influenza A. Hospitalized subjects with severe influenza A (as defined in the inclusion criteria) will be eligible for study participation. Up to 40 sites in the United States will participate in this protocol. Adults and children may participate. There is no exclusion for pregnancy.

A total of 150 eligible subjects will be randomized in a 2:1 ratio to receive either high-titer or low titer (control) anti-influenza plasma on Study Day 0 (refer to Section 5.7 – Plasma Dose). All subjects will receive standard care antivirals (generally this would be oseltamivir).

Subjects will be assessed on Study Day 0 (baseline) and on Study Days 1, 2, 3, 7, 14, and 28. For participants who are not hospitalized on Days 2, 14, and 28, contact with the participant for the purpose of study data collection on those days may be performed by telephone.

All subjects will undergo a series of efficacy, safety, and PK (HAI) assessments during the study. Blood samples will be collected on Day 0, 1, 3, and 7. OP swabs for influenza PCR will be obtained on Day 0 and 3.

4 STUDY POPULATION

4.1 Inclusion Criteria for Enrollment (Screening)

1. Subjects must be aged 2 weeks or older.
2. Hospitalization due to signs and symptoms of influenza

Note: The decision for hospitalization will be made by the treating clinician. To be considered eligible, the hospitalization may either be an initial hospitalization, or a prolongation of a hospitalization due to a respiratory illness that was found to be from influenza. Influenza could be a component of a larger respiratory syndrome (i.e. COPD exacerbation thought to be triggered by influenza). However, respiratory syndromes that are not likely due to the virus should not be included (i.e. a subject that had mild influenza then developed pulmonary embolism and respiratory distress from the embolism).
3. Study plasma available on-site or available within 24 hours after randomization.
4. Not previously screened nor randomized in this study
5. Willingness to have blood and respiratory samples obtained and stored.
6. Willingness to return for all required study visits and participate in study follow up.

4.2 Inclusion Criteria for Randomization

1. Locally determined positive test for influenza A (by PCR, other nucleic acid testing, or by rapid Ag) from a specimen obtained \leq 48 hours prior to randomization.
2. Onset of illness \leq 6 days before randomization, defined as when the subject first experienced at least one respiratory symptom or fever.

Note: For subjects with chronic respiratory symptoms (chronic cough, or COPD with baseline dyspnea), the onset of symptoms is defined as the point when the symptoms changed during this illness).
3. Hospitalized due to influenza, with anticipated hospitalization for more than 24 hours after randomization. Criteria for hospitalization will be up to the individual treating clinician.
4. NEW or PEW score \geq 3 within 12 hours prior to randomization.
5. ABO-compatible plasma available on-site or available within 24 hours after randomization.

4.3 Exclusion Criteria for Randomization

Subjects who meet any of the following criteria will be excluded from study participation:

1. Strong clinical evidence in the judgment of the site investigator that the etiology of illness is primarily bacterial super-infection in origin. Co-infection would be allowed, as there may be benefit to resolving influenza illness faster. Super-infection, where influenza illness occurred and is resolving, and new bacterial illness causing deterioration should be excluded. (e.g., if the subject's respiratory infection is thought unlikely to benefit from additional antiviral therapy, this exclusion criteria would be met).
2. Prior treatment with any anti-influenza investigational drug, anti-influenza investigational IVIG, or anti-influenza investigational plasma therapy within 30 days prior to screening. Other investigational drug therapies (non-influenza) and administration of plasma and/or IVIG for non-influenza reasons are allowed.
3. History of allergic reaction to blood or plasma products (as judged by the site investigator).

4. A pre-existing condition or use of a medication that, in the opinion of the site investigator, may place the individual at a substantially increased risk of thrombosis (e.g., cryoglobulinemia, severe refractory hypertriglyceridemia, or clinically significant monoclonal gammopathy). Prior IVIG use alone would not meet exclusion criteria, but the investigator should consider the potential for a hyper-coagulable state.
5. Subjects who, in the judgment of the site investigator, will be unlikely to comply with the requirements of this protocol, including being uncontactable following discharge from hospital.
6. Medical conditions for which receipt of 450-700 mL (or pediatric equivalent) of intravenous fluid may be dangerous to the subject (e.g., decompensated congestive heart failure).

